5.2.4.2. Analysis Methods

OS analysis will be based on safety population. The Kaplan-Meier method will be used to estimate the distribution of OS. Median OS with 95% CI will be provided. In addition, the number and percentage of subjects who died or were censored will be reported. Additionally, the survival rate with 95% CI at 3, 4, 5, 6-years will be estimated using Kaplan-Meier method. The Kaplan-Meier OS curve will also be plotted.

5.3. Efficacy-related Laboratory Assessments

Efficacy-related laboratory assessments of ESR, CRP, and fibrinogen will be summarized by descriptive statistics at baseline and each scheduled timepoint. The changes from baseline results will also be summarized.

5.4. Patient-reported Outcomes

The MCDSS questionnaire will only be completed by the sub-population from the C0328T03 study. The reliability of the MCDSS will be assessed by collecting the completed questionnaire 3 times during the extension study: at the start of the screening visit, and predose at Cycles 1 and 2.

The patient-reported MCDSS total score at each timepoint and the change from baseline in MCDSS total score will be summarized.

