**Efficacy Analyses**

The proportion of previously responding subjects and siltuximab-naïve subjects who maintain disease control will be summarized, as will the duration of disease control and survival. In addition, the MCDSS total score and the change from baseline in MCDSS total score will be summarized.

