### **Patient-reported Outcomes**

The MCDSS will be assessed only in the subjects previously treated in the C0328T03 study, to provide an independent assessment of the scale designed for the CNTO328MCD2001 study ([Vernon et al, 2009](#)). The scale, developed based on results of qualitative research with MCD patients and clinical experts, was subsequently field tested with additional MCD patients. Symptom presence/absence and severity are noted on an anchor-based numeric scale. Frequency of occurrence can be generated when the instrument is used as a daily record of symptoms, as the recall period is 24 hours. Completion time is approximately 5 minutes. A summary score is generated based on the scores of 0 (very mild) to 5 (very severe). See Section 9.3.4 for additional information.

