#### **9.3.4 Patient-reported Outcomes**

The MCDSS questionnaire will only be completed by the sub-population from the C0328T03 study. The reliability of the MCDSS will be assessed by collecting the completed questionnaire 3 times during the study: at the start of the screening visit, and predose at Cycles 1 and 2.

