#### **11.5 Glycoform Analysis and In Vivo Protein Degradation**

These analyses will be reported in a separate technical report.

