1.1. Overview of Trial Design

This is an open-label, multicenter, non-randomized Phase 2 study designed to study the safety of extended treatment with siltuximab in subjects who were previously enrolled in sponsor-initiated studies of multicentric Castleman's disease (MCD) (C0328T03 and CNT0328MCD2001) and are either siltuximab-naive or have not progressed on siltuximab in the opinion of the investigator.

The primary objective is to evaluate the long-term safety of siltuximab in subjects with MCD. The secondary objectives are

- To determine the proportion of previously responding subjects who maintain disease control
- To determine the proportion of siltuximab-naive subjects who experience disease control
- To describe the duration of disease control and survival
- To assess reliability of a multicentric Castleman's disease symptom scale (MCDSS)
- To evaluate IL-6 levels
- To assess formation of antibodies to siltuximab (immunogenicity) after long-term treatment in the MCD population

Up to 75 subjects will be eligible for the study, the majority of whom will be on active therapy with siltuximab and have not progressed at the time of enrollment. Subjects with unmanageable toxicity or discontinuation of treatment from previous sponsor-initiated siltuximab studies due to an adverse event, progression of disease, or withdrawal of consent will be excluded.

Siltuximab will be given as a 1 hour infusion of 11 mg/kg every 3 weeks. The treatment interval may be lengthened to 6 weeks at the investigator's discretion for subjects with confirmed partial or complete response of more than 6 months duration. During the study, no dose modifications of siltuximab will be allowed. Dose delays of up to 3 weeks will be allowed for treatment-related toxicity. Documentation of dose delays, including the reason for delay, is required. All subjects will be treated until they progress, withdraw, experience unacceptable toxicity, or until the 6-year data cutoff, whichever comes first.

Throughout the study, investigator assessment of disease control will be collected during screening, at Cycles 4, 7 and 10, every 6 months thereafter, and at study treatment discontinuation. Laboratory assessments for erythrocyte sedimentation rate (ESR), CRP, and fibrinogen will also be performed at these same timepoints. Safety evaluations will

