2.5. Imputation of Partial Dates

Unless specified otherwise, no data imputation will be applied for missing safety and efficacy evaluations. For analysis and reporting purpose, partial dates in adverse event (AE onset date; AE end date), concomitant therapies (start date; end date), MCD diagnosis date, prior MCD therapies (start date; end date) and start date of subsequent MCD therapy will be imputed.

The detailed imputation rules along with other derived variables are specified in the data presentation specification (DPS).

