2.6. General Analysis Method

In general, continuous variables will be summarized using descriptive statistics such as mean, standard deviation (SD), median and range. Categorical variables will be summarized using frequency and percentage. For time-to-event variables, the Kaplan-Meier method will be used for descriptive summaries. For the calculation of time-to-event and duration-of-event variables, the difference between the start date and the end date plus 1 day will be used.

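### MCDSS reliability is a secondary objective, but the plan summarizes only scores and changes, so no reliability coefficient or confidence interval will be reported

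*SAP*

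**What the plan says.** **The objective.** SAP 1.1 lists among the secondary objectives "To assess reliability of a multicentric" Castleman's disease symptom scale. The Protocol Synopsis and Protocol 2 list the same objective. Protocol 3.2 says why the scale is collected in former C0328T03 subjects: "to provide an independent assessment of the scale designed for the CNTO328MCD2001 study".

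**The data.** Protocol 9.3.4 says: "The reliability of the MCDSS will be assessed by collecting the completed questionnaire 3 times during the study". The three occasions are the start of the screening visit, predose Cycle 1 and predose Cycle 2. SAP 5.4 repeats this.

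**The analysis.** SAP 5.4 and Protocol 11.4.4 share one sentence: "The patient-reported MCDSS total score at each timepoint and the change from baseline in MCDSS total score will be summarized". The Synopsis agrees: "In addition, the MCDSS total score and the change from baseline in MCDSS total score will be summarized". SAP 2.6 says what a summary means: "continuous variables will be summarized using descriptive statistics such as mean, standard deviation (SD), median and range".

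**What is absent.** Neither document names an ICC, a test-retest correlation, an internal-consistency coefficient or a standard error of measurement. Neither says which administration is the MCDSS baseline. The efficacy endpoint list in SAP 5.2 does not mention the MCDSS.

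**The concern.** The sentence that says how reliability will be assessed describes a collection schedule, not an analysis. The analysis sentence that follows treats the MCDSS as an outcome to be tracked over time rather than as an instrument to be evaluated. Mean scores and mean changes say nothing about reliability by themselves, because the same means are compatible with any test-retest agreement.

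At stake is whether a declared secondary objective gets a stated result. The independent look at the scale is the reason Protocol 3.2 gives for asking these subjects to complete it. Under the present text the report would hold the raw material for some pairs, but no estimate and no statement of its uncertainty.

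**Working it through.** The documents give no reliability figure, target or sample size, so there is no figure of theirs to reproduce. There are three checks.

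**1. What can be recovered from the planned output?** Take two administrations completed by the same n subjects. Let S1 and S2 be the SDs at the two visits, D the SD of change and m the mean change. All four are planned output for a pair that includes baseline. The two-way mean squares are then

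- between subjects: MSR = [2(S1² + S2²) − D²]/2
- error: MSE = D²/2
- visits: MSC = n·m²/2

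and the absolute-agreement, single-measurement ICC for two visits is

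ICC = (MSR − MSE) / [MSR + MSE + (2/n)(MSC − MSE)].

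A numerical check with unequal SDs and a mean shift gave the same ICC and the same F-based CI from the raw scores as from these summaries. Recovery is therefore exact, not approximate.

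The planned output does carry the signal. With equal SDs and no mean shift, D = SD × √[2(1 − r)], where r is the test-retest correlation. This is 1.18, 1.00, 0.77 and 0.45 times the score SD at r = 0.3, 0.5, 0.7 and 0.9.

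**2. Which pairs does that cover?** Three administrations make three pairs. Coverage depends on the undefined baseline:

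| Baseline | Changes reported | Pair(s) not covered |
|---|---|---|
| Screening | Cycle 1 − screening; Cycle 2 − screening | Cycle 1 vs Cycle 2 |
| Predose Cycle 1 | Cycle 2 − Cycle 1 | Screening vs Cycle 1; screening vs Cycle 2 |

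The pairs are not interchangeable. The questionnaire is completed before dosing at Cycles 1 and 2, so Cycle 1 to Cycle 2 always contains the Cycle 1 infusion. Screening to predose Cycle 1 contains no dose of this trial. It may still contain a parent-study dose: Protocol 3.1 expects most subjects to be on siltuximab at enrollment, and Table 1 allows screening on Days −28 to 0, about 1 to 29 days before Day 1. A dose that shifts scores lowers an absolute-agreement ICC. Starting from 0.80, a mean shift of d score SDs gives 0.80/(1 + d²/2), which is 0.78 at d = 0.2 and 0.71 at d = 0.5. If baseline is predose Cycle 1, the pair without a dose of this trial is one of those that cannot be recovered.

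**3. How precise would a stated ICC be?** Every n and every observed ICC here is an assumption. For two visits with MSC = MSE, let F0 = MSR/MSE = (1 + ICC)/(1 − ICC), which is 9 at ICC 0.80. The 95% limits are

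- lower = (F0 − FL)/(F0 + FL), FL = 97.5th percentile of F(n − 1, v)
- upper = (F0·FU − 1)/(F0·FU + 1), FU = 97.5th percentile of F(v, n − 1)

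with v the Satterthwaite degrees of freedom. At ICC 0.80, v = 81/[a² + b²/(n − 1)], where a = 8/n and b = 1 + 8(n − 1)/n.

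| Assumed n | v | FL | FU | 95% CI |
|---|---|---|---|---|
| 8 | 7.99 | 4.53 | 4.90 | 0.33 to 0.96 |
| 12 | 11.99 | 3.32 | 3.43 | 0.46 to 0.94 |
| 15 | 14.99 | 2.89 | 2.95 | 0.51 to 0.93 |
| 23 | 22.99 | 2.33 | 2.34 | 0.59 to 0.91 |

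For an observed 0.60 the interval is −0.07 to 0.90 at n = 8 and 0.26 to 0.81 at n = 23. For 0.90 it is 0.62 to 0.98 and 0.78 to 0.96. Using all three administrations at ICC 0.80 gives 0.50 to 0.95 and 0.65 to 0.90. The 23 is the Castleman's group described in Protocol 1.1.2.1, which includes unresectable localized disease. This trial requires multicentric disease, so 23 is illustrative only.

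**The case against.** The best defence is that the study is descriptive, and that the planned tables already determine a two-way ICC and its CI for any pair that includes baseline. That is correct given the same subjects at both visits. A reader might infer that the planned summaries bear on reliability only loosely, or that unequal SDs at the two visits would defeat the calculation. The documents do not support either reading, because the SD at each timepoint is itself planned output. What remains is that no coefficient or interval is stated, one or two pairs are not covered, and which ones depends on an undefined baseline.

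Other replies carry less weight.

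- *It may be reported elsewhere.* Protocol 11.5 says of the glycoform work: "These analyses will be reported in a separate technical report". Nothing similar is said of the MCDSS. SAP 2.5 sends imputation rules and derived variables to a data presentation specification. That document, which is not available here, could define baseline, but nothing suggests it holds a reliability analysis.
- *No hypothesis testing is planned.* An ICC with a CI is estimation. The SAP already plans 95% CIs for duration of disease control and for survival.
- *Reliability need not mean test-retest.* True, the objective does not say. Three administrations close together point to test-retest, and internal consistency cannot be obtained from total scores.
- *Naming a pair now is not real pre-specification.* The scale is given only around study entry, and the SAP already uses the 6-year cutoff brought in by the last amendment, so the scores may have been in hand when it was written. That limits the protection gained from naming a pair. It does not remove the need for a stated result.

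**Conclusion.** The point holds as a gap between a declared secondary objective and its analysis: the plan, followed exactly, states no MCDSS reliability coefficient and no CI. It should be corrected, but it is limited. It concerns one descriptive objective in an unstated number of former C0328T03 subjects. Safety, disease control and survival results do not depend on it.

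The documents do not support saying that reliability could not be learned from the report, since exact recovery is possible for baseline pairs with the same subjects. Nor do they support treating the two adjacent pairs as equally suitable, since only Cycle 1 to Cycle 2 is certain to contain a dose of this trial.

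The absence of a coefficient rests on the text alone. The precision figures rest on assumed n, assumed observed ICCs and no visit effect beyond error. They show that the estimate could be too imprecise to judge the scale, which is a reason to print the interval.

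**What to change.** In SAP 5.4, keep the descriptive summaries and add:

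1. A test-retest ICC (two-way, absolute agreement, single measurement) on the MCDSS total score, with two-sided 95% CI and the number of subjects contributing.
2. The standard error of measurement, SD × √(1 − ICC). At an ICC of 0.80 this is 0.45 score SDs.
3. Screening versus predose Cycle 1 as the main pair, with the retest interval in days and whether a parent-study siltuximab dose fell on or after the screening questionnaire.
4. Cycle 1 versus Cycle 2, or the three-administration ICC, as supportive, noting that the Cycle 1 dose lies within it.
5. Which administration is the MCDSS baseline, or a reference to the data presentation specification if it is defined there.

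The cost is a few lines of text and a short program. The total scores are already collected. Visit dates give the interval, and SAP 2.4 and 4.3 already draw on siltuximab administrations from the parent and extension studies. The one drawback is that the interval may be wide.

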6. SAFETY

Safety analyses will be based on safety population. Safety evaluation will focus on AEs, clinical hematology and chemistry laboratory tests. The overall safety of long-term treatment with siltuximab will be assessed via evaluation of AEs occurred from both parent study and extension study. In the long-term safety extension study, safety monitoring will consist of continuous AE reporting with a focus on infections, hyperlipidemia, neutropenia, thrombocytopenia, GI perforations, infusion-related reactions, liver function, and immunogenicity.

6.1. Adverse Events

All adverse events, regardless of seriousness, severity, or presumed relationship to study therapy, will be recorded in standard medical terminology. All toxicities will be graded according to graded according to the National Cancer Institute Common Terminology Criteria for Adverse Events (NCI-CTCAE), Version 4.0. For AE reporting, the verbatim term used in the CRF by investigators to identify adverse events will be coded to a system organ class (SOC) and a preferred term (PT) using the latest version of Medical Dictionary for Regulatory Activities (MedDRA) coding dictionary.

Unless otherwise specified, at each level (e.g., system organ class and/or preferred term) of subject summarization in reporting the incidence of the AE, a subject is counted once if one or more events were recorded.

All summaries of AEs will be based on treatment-emergent adverse events (TEAEs). TEAEs are defined as any AE that occurs after start of the first siltuximab through 30 days after the last study siltuximab treatment; or the day prior to start of subsequent anticancer therapy, whichever is earlier; or any AE that is considered drug-related (very likely, probably, or possibly related) regardless of the start date of the event; or any AE that is present at baseline but worsens in toxicity grade or is subsequently considered drug-related by the investigator.

The incidence of TEAEs will be summarized overall, by MedDRA system organ class (SOC) and preferred term, by toxicity grade, by relationship to siltuximab treatment, and by number of years of siltuximab exposure. Specifically, the following AE summaries will be presented:

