Prolonged exposure at siltuximab dose levels ranging from 3 to 12 mg/kg was observed in this study, with no dose-limiting toxicity (DLT) observed after a median exposure of 331 days (range up to 1148 days). Three (3) subjects had Grade 3 or higher AEs (nausea, upper respiratory tract infection, vomiting, hypertriglyceridemia, and hypertension), which were considered unrelated to treatment with siltuximab by the study investigators. Serious adverse events (SAEs) were reported in 6 of 23 subjects, and none were attributable to siltuximab. Mild infusion reactions (eg, light-headedness, flushing,

hypertension, hives) were observed in 3 subjects, but siltuximab was not discontinued due to these events. No treatment-related deaths have been reported.

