## 6 DOSAGE AND ADMINISTRATION

Siltuximab will be given as a 1-hour infusion at 11 mg/kg every 3 weeks. All subjects will be treated until they progress, withdraw, experience unacceptable toxicity, or until the 6-year data cutoff, whichever comes first. A data cutoff will occur approximately 6 years after the start of enrollment; however, continued drug supply will be ensured for study subjects who would not otherwise have access to siltuximab.

Subjects with confirmed partial or complete remission, defined as a documented radiographic response, for more than 6 months (including those entering the study in PR or CR) may be dosed every 6 weeks at the investigator's discretion. Demonstration of radiographic response is not required for subjects with skin-only disease with confirmed PR/CR for more than 6 months. Subjects on the 6-week schedule should be monitored for safety and disease assessment evaluations as per protocol Time & Events Schedules (see [Table 1](#) and [Table 2](#)). When disease progression is suspected, all screening and pre-dose Cycle 1 evaluations should be repeated and treatment with siltuximab could continue at 11 mg/kg siltuximab every 3 weeks. The effective switch from the 3-week dosing schedule to the 6-week schedule can only occur on odd-numbered cycle visits to match the collection timepoints of biomarkers and immunogenicity samples of every 12 weeks, and has to occur on dosing days. Switching back to a 3-week schedule upon suspected disease progression can occur at any cycle visit.

During the study, no dose modifications of siltuximab will be allowed. Dose delays of up to 3 weeks will be allowed for treatment-related toxicity. Documentation of dose delays, including the reasons for the delay, is required.

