## 9 STUDY EVALUATIONS

### 9.1 Study Procedures

#### 9.1.1 Overview

The Time and Events Schedules (see [Table 1](#) and [Table 2](#)) that follow the Synopsis summarizes the frequency and timing of safety, efficacy, pharmacodynamic biomarker, and other evaluations applicable to this study. Enrolled subjects will be assessed for eligibility according to the inclusion and exclusion criteria (see [Section 4.2](#) and [Section 4.3](#)).

Additional serum or urine pregnancy tests may be performed, as determined necessary by the investigator or required by local regulation, to establish the absence of pregnancy throughout the study. The total blood volume to be collected from each subject will depend on the amount of time they participate in this long-term study. The table in [Attachment 3](#) shows the maximum volume per each assessment. PRO assessments (ie, MCDSS) during a visit should be conducted before any tests, procedures, or other consultations for that visit.

The assessments per visit will vary as indicated per Time and Events schedules (see [Table 1](#) and [Table 2](#)). The required assessments at every dosing visit are:

- Weight
- Vital signs
- Review of adverse events
- Review of concomitant medications
- Administration of siltuximab

The follow-up Week 4 assessment (4 weeks after the last dose) will be considered as the end of treatment visit. During this visit, assessments will be repeated according to the Time & Events Schedules (see [Table 1](#) and [Table 2](#)) to conclude the study treatment and obtain follow-up details. The remainder of the follow-up period constitutes 2 visits, 8 and 12 weeks after the last administration during which serum blood samples will be collected to assess immunogenicity (antibodies to siltuximab) and biomarkers as applicable.

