## **12.2 Procedures**

### **12.2.1 All Adverse Events**

All adverse events, whether serious or non-serious, will be reported from the time a signed and dated informed consent form is obtained until 30 days after last study agent administration. The only exception is for subjects who have withdrawn informed consent for study participation or for subjects who have received additional treatment with therapeutic intent for MCD within 30 days after the last study agent administration. For subjects who have received additional treatment with therapeutic intent for MCD during the AE reporting period, only AEs that are considered to be possibly, probably, or definitely related to study agent must be reported (unless the subject has been withdrawn from the study). Serious adverse events, including those spontaneously reported to the investigator within 30 days after the last dose of study drug, must be reported using the Serious Adverse Event Form. The sponsor will evaluate any safety information that is spontaneously reported by an investigator beyond the time frame specified in the protocol. Key safety events of interest (see the current Investigator's Brochure), including infections, hyperlipidemia, neutropenia, thrombocytopenia, GI perforations, infusion-related reactions, liver enzyme abnormalities, and immunogenicity.

After the 6-year data cutoff, subjects who do not have access to commercially available siltuximab may continue to receive treatment provided by the Sponsor. For these subjects only, SAEs (information on study agent administration and concomitant medications use to treat the SAEs) and pregnancies will have to be reported and collected after the data cutoff at 6 years. These events will be reported to the appropriate health authorities in safety update reports.

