6.1.7. TEAEs Leading to Discontinuation of Siltuximab Treatment

A summary of number of subjects who discontinued siltuximab treatment because of 1 or more TEAEs by MedDRA system-organ class and preferred term will be provided. The summaries will be presented by all Grades and Grade 3 or higher. This table includes associated TEAEs for those subjects who discontinued siltuximab treatment due to an adverse event reported on the “End of Treatment” CRF page.

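### On 6-week dosing, a new unrelated-rated AE with onset on days 31 to 42 after the last dose is a TEAE if the next dose is given, but not if the AE ends treatment

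*SAP*

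**What the plan says.** **TEAE window.** SAP 6.1 bases every AE summary on TEAEs and defines them so: "TEAEs are defined as any AE that occurs after start of the first siltuximab through 30 days after the last study siltuximab treatment". The window closes sooner if subsequent anticancer therapy starts. Two further clauses extend it. A drug-related AE counts whatever its start date, and so does a baseline AE that worsens in grade or is later judged drug-related. SAP 2.4 takes the last dose to be the latest non-zero dose given in the extension study.

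**Dosing interval.** Protocol section 6 sets 3-week dosing, but subjects with a confirmed response lasting more than 6 months "may be dosed every 6 weeks" if the investigator chooses; SAP 1.1 repeats this. Neither document adjusts the TEAE window for the longer interval.

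**Discontinuation outputs.** SAP 6.1.7 says: "This table includes associated TEAEs for those subjects who discontinued siltuximab treatment due to an adverse event". SAP 4.2 tabulates the reasons for stopping treatment from the End of Treatment CRF page and plans a listing that names the AE responsible. It does not restrict that AE to TEAEs.

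**Protocol counterpart.** Protocol 11.3 also uses 30 days after the last dose, within the 6-year cutoff, but has none of the SAP's further clauses. Protocol 12.2.1 says that adverse events "will be reported from the time a signed and dated informed consent form is obtained until 30 days after last study agent administration".

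**The concern.** The window is anchored on a date fixed only by what happens next. On day 36 of a 6-week interval the subject is on schedule. If the next dose is given, that day lies between first and last dose and an AE starting then is counted. If the AE leads to stopping, the previous dose becomes the last dose, and the AE falls 6 days outside the window. Inclusion therefore depends on the very outcome that SAP 6.1.7 is meant to describe.

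The exclusion can only lower counts, and it falls on long-term responders in a study whose primary objective is long-term safety. Besides SAP 6.1.7, it can reach the Grade 3 or 4 table (6.1.3), the SAE table (6.1.5), deaths due to TEAEs (6.2.2) and Grade 3 or 4 infections (6.3.2). Because SAP 4.2 does not apply the TEAE filter, one report could give two different counts of AE discontinuations with no rule to explain the difference.

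**Working it through.** The plan gives no figure of its own to reproduce. The check is day arithmetic plus a direct application of the SAP 6.1 rule.

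**Inputs.** Window after last dose: 30 days (SAP 6.1). Intervals: 21 and 42 days (Protocol 6). Dosing visit window: minus 3 to plus 4 days (Protocol Table 1, footnote a). Maximum enrolment: 75 (Protocol 11.2).

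**Step 1: uncovered days in the final interval** = max(0, interval − 30).

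- 3-week dosing: 21 − 30 < 0, so 0 days; also 0 at 21 + 4 = 25 days.
- 6-week dosing: 42 − 30 = 12 days (days 31 to 42); 12/42 = 28.6%.
- 6-week dosing at the edges of the Table 1 visit window: 39 − 30 = 9 days (9/39 = 23.1%) and 46 − 30 = 16 days (16/46 = 34.8%).

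**Step 2: the rule applied to a new AE rated unrelated, 6-week dosing.** If the day-42 dose is given, the window runs to at least day 42 + 30 = 72.

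| Onset, days after most recent dose | Treatment stops | Day-42 dose given |
|---|---|---|
| 30 | TEAE | TEAE |
| 31 | not a TEAE | TEAE |
| 35 | not a TEAE | TEAE |
| 42 | not a TEAE | TEAE |

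If the AE is rated drug-related, or was present at baseline and worsened, it is a TEAE in every cell.

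**Step 3: scale.** Only each subject's final interval is affected. The documents do not say how many subjects are on 6-week dosing at their last dose. Assuming 10% to 100% of 75:

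- 7.5 × 12 = 90 person-days (about 3 patient-months)
- 75 × 12 = 900 person-days (about 30 patient-months)

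Against an assumed 2 to 6 years of treatment, 12 days is 12/730.5 = 1.6% down to 12/2,191.5 = 0.5% of one subject's follow-up. On the other side, one event among 75 subjects is 1/75 = 1.3 percentage points.

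**The case against.** The best defence is that the gap is short, confined to one interval per subject, and sits in a descriptive study with no hypothesis test. The events also remain visible elsewhere: SAP 4.2 can name the AE that led to stopping, SAP 6.2.1 tabulates all deaths without a window, and SAP 6.3.3 lists secondary malignancies. All of this is correct. It limits the importance of the point but does not remove the outcome-dependent rule or the possible mismatch between SAP 4.2 and 6.1.7.

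Several stronger readings are tempting, and the documents do not support them.

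- **Dose delays widen the gap to 33 of 63 days (52%), or open a 12-day gap on 3-week dosing.** Protocol 6 says: "Dose delays of up to 3 weeks will be allowed for treatment-related toxicity". A related AE behind such a delay is a TEAE under SAP 6.1 whatever its date. Protocol 6.1 and 6.1.1 give other grounds for delay, but an event that causes a delay begins before the dose is due: by about day 21 on 3-week dosing, which is inside the window, and by about day 42 on 6-week dosing. Only a second, new, unrelated event during the delay could fall in the extra days.
- **About 29% of AE discontinuations are lost.** The 28.6% is a share of days. It would be a share of discontinuations only if every causal AE were new, rated unrelated, and began uniformly over the final interval. An AE that began by day 30 and later ended treatment counts in full.
- **The events are never collected.** Reporting ends at day 30 and Protocol 9.1.1 states: "The follow-up Week 4 assessment (4 weeks after the last dose) will be considered as the end of treatment visit". But on day 36 nobody yet knows that the last dose has been given. AE reporting is continuous and AEs are reviewed at each dosing visit, so the event would ordinarily be in the database. The defect lies in tabulation.
- **The drug-related clause rescues almost nothing.** Protocol 1.1.2.1 reports of C0328T03: "Serious adverse events (SAEs) were reported in 6 of 23 subjects, and none were attributable to siltuximab". That describes SAE attribution in a parent study, not AEs that end 6-week dosing here. Under Protocol 12.1.2, a rating of possible needs only that a causal link cannot be ruled out.

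**Conclusion.** The point holds in a narrow form. On 6-week dosing, a new, unrelated-rated AE with onset on days 31 to 42 of the final interval is in or out of the TEAE tables according to whether it ended treatment. The gap is 12 of 42 days (28.6% of that interval), or 9 to 16 days across the Table 1 visit window. It is zero on undelayed 3-week dosing, and any error is towards fewer events.

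This assumes that the event is recorded at the visit where treatment is stopped and that SAP 6.1 is applied as written. The number of events lost cannot be computed, because neither the number of subjects on 6-week dosing nor the AE rates are given; it may be none. A reader might infer that a large share of discontinuations disappears, or that the AE reporting period and visit schedule must be amended. The documents support neither. This is a worthwhile SAP correction, not a threat to the study's conclusions.

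Separately, Protocol 11.3 has no drug-related clause, so under it even a related AE after day 30 is left out. The two definitions need to be reconciled.

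**What to change.** In SAP 6.1:

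1. End the window at the later of (a) 30 days after the last dose and (b) the date of the decision to stop treatment, still closing the day before subsequent anticancer therapy.
2. Count any AE recorded as the reason for discontinuation on the End of Treatment CRF page as a TEAE whatever its onset day, so that SAP 6.1.7 agrees with SAP 4.2.
3. Name the CRF date that serves as the decision date. SAP 4.2 mentions a discontinuation date, and if that field holds the last dose date it will not close the gap.
4. State how this definition relates to Protocol 11.3 and which one governs the report.

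For the example above, a day-36 onset with a stop decision on day 42 is then counted, as it would be if dosing had continued.

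The cost is SAP wording, slightly higher event counts, and a window whose length varies between subjects and needs a table footnote. The stop date still depends on the subject's course, but the window no longer excludes the AE that caused the stop. No dosing rule, visit or AE reporting period has to change.
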